**Combined 20130356, 20110100 & 20140159 studies**

**Proportion of subjects achieving the secondary endpoints of  $\geq 30\%$  reduction in iPTH from day 1 of cinacalcet treatment to mean value during weeks 11 and 15 will be reported with 95% CI for all efficacy analysis set subjects. Subjects who have no weeks 11 or 15 iPTH values will be considered non-responders.**

**Proportion of subjects achieving the secondary endpoints of  $\geq 30\%$  reduction in iPTH from day 1 of cinacalcet treatment to mean value during weeks 23 and 28 will be reported with 95% CI for all efficacy analysis set subjects. For subjects who do not have an iPTH value during weeks 23 and 28, the mean of the last two available post-baseline values collected at protocol-specified visits in the dose titration phase will be used. If only one post-baseline value is available, this single value will be used. If no post-baseline value is available, the subject is considered a non-responder.**

**Summary statistics will be provided for percent change in iPTH, change in serum cCa and change in serum phosphorus over time from day 1 of cinacalcet treatment for all efficacy analysis set subjects.**

**10.6.2 Sensitivity Analysis of Secondary Endpoints**

**Sensitivity Analysis of the effect of dose interruption (final analysis only)**

**To study the effect of dose interruption, sensitivity analyses will be performed separately for subjects in the efficacy analysis set who have and do not have dose interruption of  $> 14$  days between EOIP of the parent study and Study Day 1 in study 20140159. Secondary endpoints of achievement of  $\geq 30\%$  reduction from day 1 of cinacalcet treatment to mean iPTH during weeks 11 and 15, and percent change in iPTH over time from day 1 of cinacalcet treatment will be analyzed using combined 20130356, 20110100 and 20140159 studies data.**

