# 2.5 Studies Eligible to Roll-over to 201401592.5.1 Amgen Study 20130356

Amgen Study 20130356 is a phase 3 randomized, multicenter, open-label, controlled study. In Study 20130356, cinacalcet is being evaluated in pediatric subjects enrolled between the ages of 6 and < 18 years, with SHPT and CKD receiving either

CONFIDENTIAL

Page 16 of 79

**AMCEN**"

hemodialysis or peritoneal dialysis. Approximately 48 subjects are planned to be randomized into the study to one of two treatment arms in a 1:1 allocation ratio; daily oral administration of cinacalcet in addition to SOC or SOC only. Once randomized, the expected treatment period in 20130356 is 20 weeks with a 4-week safety follow-up period. Subjects who are eligible for and enroll in the 20140159 extension study will do so at the completion of the 20-week treatment period in 20130356 or following Study 20130356 termination and within 7 days of day 1 of 20140159, unless there is an administrative delay. The end of study (EOS) procedures for an individual subject will occur at the same time as the end of investigational product (EOIP) visit for subjects enrolling in Study 20140159. The 4-week safety follow-up period in 20130356 will not apply for these subjects.

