# 2.5.2 Amgen Study 20110100

Amgen Study 20110100 is a phase 2, multicenter, open-label, single-arm study. In Study 20110100 cinacalcet is being evaluated in pediatric subjects enrolled between the ages of 28 days and < 6 years, with SHPT and CKD receiving either hemodialysis or peritoneal dialysis. The expected treatment period in 20110100 is 24 weeks of daily oral administration of cinacalcet in addition to SOC with a 2-week safety follow-up period. Subjects who are eligible for and enroll in the 20140159 extension study will do so at the completion of the week 26 End of Study visit or at Study 20110100 termination and within 7 days of day 1 of 20140159 unless there is an administrative delay. For subjects enrolled in the 20140159 extension study at the time of 20110100 study termination, the 2-week safety follow-up period in 20110100 will not apply for these subjects and the EOS procedures for an individual subject will occur at the time as the EOIP visit for subjects enrolling in Study 20140159.

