**Day 1 of cinacalcet treatment (combined studies 20130356, 20110100 and 20140159)**

The date that the initial dose of cinacalcet treatment is administered in studies 20130356, 20110100 or 20140159.

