**Secondary endpoints for combined 20130356, 20110100 and 20140159 studies**

Secondary endpoint	Sensitivity Analyses	Planned for Interim or Final analysis
Achievement of $\geq 30\%$ reduction from day 1 of cinacalcet treatment to mean iPTH during weeks 11 and 15	IPW:  The missingness model will include baseline iPTH, cCa, phosphorus, age group at first cinacalcet dose, sex, race, and AEs of nausea, vomiting and symptomatic hypocalcemia. Dialysis vintage, AE or IPD related to ending IP may be also included in the model depending on the EOIP reason observed in the study.  Completer analysis:  Only enrolled subjects who completed 15 weeks from Day 1 of cinacalcet treatment will be included in the analysis. Subjects with no iPTH values during weeks 11 and 15 since Day 1 of cinacalcet treatment will be considered as nonresponders.	Final analysis only
	Per protocol analysis:  Subjects from the per protocol set for combined 20130356, 20110100 and 20140159 studies and with at least one iPTH value during weeks 11 and 15 will be used.	Final analysis only
	Nearest 2 imputation  If no values are observed during weeks 11 and 15 from Day 1 of cinacalcet treatment, the nearest two values at or after week 7 from Day 1 of cinacalcet treatment will be used, including unscheduled visit values, values prior to or after weeks 11 and 15. Subjects with no observed values at or after week 7 will be considered nonresponders.	Final analysis only

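### For cinacalcet-treated subjects who completed parent treatment, the responder endpoint in the dose-interruption sensitivity analysis is measured before the interruption can begin

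*SAP*

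**What the plan says.** SAP 10.6.2 plans, for the final analysis only, separate analyses of Efficacy Analysis Set subjects with and without a dose interruption. The interruption is one of more than 14 "days between EOIP of the parent study and Study Day 1 in study 20140159". Two secondary endpoints are analysed on the combined three-study data: the 30% "reduction from day 1 of cinacalcet treatment to mean iPTH during weeks 11 and 15, and percent change in iPTH over time".

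The clock starts at day 1 of cinacalcet treatment, which SAP 6.2 defines as "The date that the initial dose of cinacalcet treatment is administered in studies 20130356, 20110100 or 20140159". The completer row of the combined-studies table in SAP 10.6.2 counts weeks on that clock: "Subjects with no iPTH values during weeks 11 and 15 since Day 1 of cinacalcet treatment will be considered as nonresponders".

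On parent-study duration, Protocol 2.5.1 says "expected treatment period in 20130356 is 20 weeks with a 4-week safety follow-up period", and Protocol 2.5.2 says "The expected treatment period in 20110100 is 24 weeks of daily oral administration of cinacalcet", followed by two weeks of safety follow-up. Inclusion criteria 104 and 108 also admit subjects who were on study when a parent study was terminated.

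The Efficacy Analysis Set (SAP 7.3) requires a cinacalcet dose and a later assessment in 20140159. It does not require cinacalcet in the parent study. The combined weeks 23 and 28 responder endpoint exists in SAP 10.6.1 but is not part of this sensitivity analysis.

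**The concern.** An outcome can show the effect of an interruption only if it is measured during or after it. Here the split depends on what happens after parent treatment ends, while the responder endpoint is read at weeks 11 and 15 of cinacalcet. For a subject who took 20 or 24 weeks of cinacalcet in the parent study, those weeks are already past.

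At stake is the reading of the table. Similar responder rates could be reported as evidence that interruption does not matter, and different rates as evidence that it does. Among completers, neither would follow. Subjects who never had cinacalcet to interrupt add a second source of blur, because the section does not say which group they join.

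**Working it through.** **Inputs**
- iPTH targets and windows, SAP 6.2: week 11, day 78 (65–92); week 15, day 106 (93–120); week 23, day 162 (149–176); week 28, day 197 (177–211). These are defined for 20140159 study days. I assume that they carry over to cinacalcet days, since the SAP gives no separate table.
- Parent treatment: 20 weeks (20130356) and 24 weeks (20110100), with the 20110100 End of Study visit at week 26.
- Planned numbers: 48 and 30 (SAP 3.2), with 1:1 allocation in 20130356 (Protocol 2.5.1).

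**1. Reproduce the plan's figures.** Target day = 7 × week + 1 gives 78, 106, 162 and 197 for weeks 11, 15, 23 and 28, as in the SAP. Planned size: 48 + 30 = 78, as stated.

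**2. Earliest start of the gap for completers.** EOIP falls on 7 × 20 + 1 = day 141 (20130356) and 7 × 24 + 1 = day 169 (20110100).

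**3. Margin after the week-15 window.** 141 − 120 = 21 days and 169 − 120 = 49 days. If the EOIP visit is 3 days early, the margins are 18 and 46 days. Both endpoint weeks lie before the gap.

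**4. Subjects rolled over at early parent termination.** Taking a 15-day gap, the shortest that qualifies, and target days 78 and 106:

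| EOIP at cinacalcet week | Week 11 | Week 15 |
|---|---|---|
| 8 or earlier | after gap | after gap |
| 9–10 | in gap | after gap |
| 11–12 | before gap | after gap |
| 13–14 | before gap | in gap |
| 15 or later | before gap | before gap |

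The documents do not say how many such subjects there are. Their share of the interrupted group could be anywhere from 0% to 100%.

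**5. SOC arm.** 48 / 2 = 24 planned, and 24 / 78 = 31%. Under SAP 6.3 their baseline at first cinacalcet dose is their extension baseline, so their weeks 11 and 15 follow rollover, with no earlier cinacalcet to interrupt.

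**6. Would combined weeks 23 and 28 serve instead?** With a gap of g days, the extension week-3 sample falls on cinacalcet day 141 + g + 21 = 162 + g (20130356) or 169 + g + 21 = 190 + g (20110100).
- At g = 15 these are days 177 and 205, both inside the week-28 window.
- The week-3 sample stays inside that window (to day 211) only if g ≤ 211 − 162 = 49 days (20130356) or g ≤ 211 − 190 = 21 days (20110100).
- Week 23 (day 162) precedes EOIP (day 169) for 20110100 completers. For 20130356 completers the window ends on day 176, one day before the earliest nominal week-3 sample, so it can hold at best a pre-dose sample from the end of the gap.

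**7. Extension weeks 11 and 15.** These are study days 78 and 106 counted from Study Day 1. Study Day 1 ends the gap, so both are post-gap for every subject.

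**The case against.** The strongest reply is that the interrupted group may consist largely of subjects affected by parent-study termination. The extra screening procedures for an interval above 14 days are written for them (Table 4, footnote 2). For 20130356 completers, EOIP and Day 1 are the same visit unless there is an administrative delay (Protocol 3.1.1). If the interrupted subjects mostly had short parent exposure, weeks 11 and 15 could be informative. This stands as far as it goes: it rules out saying that the endpoint cannot show an interruption effect. It does not rescue the endpoint, which would pool outcomes fixed before the gap with outcomes that follow it, and no rule separates them. Completers can also enter the interrupted group. For 20110100 the nominal interval from week 24 to week 26 is 183 − 169 = 14 days, so one day of slippage crosses the cut.

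Second, percent change over time covers extension visits, so the analysis as a whole is not uninformative. That stands, and the point is confined to the responder endpoint.

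Third, SAP 7.3 presents results by parent-study treatment as well as overall, so SOC-arm subjects can be separated. That stands too. A reader might infer that they dilute the no-interruption group, but SAP 10.6.2 does not say where they go. On visit dates alone, an SOC subject with an administrative delay could even be classed as interrupted.

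Finally, all of this is descriptive, untested and secondary in a study whose primary endpoint is safety. That limits the consequences but does not change the timing.

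**Conclusion.** The point holds for cinacalcet-treated subjects who completed parent treatment. Their weeks 11 and 15 response is fixed about 21 days (20130356) or 49 days (20110100) before a gap can begin, so a difference between groups reflects selection or chance.

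A reader might go further and infer that this is true of every parent-study completer, or that the endpoint can never register an interruption. The documents do not support either. SOC-arm completers start cinacalcet in the extension, and subjects enrolled at early parent termination with less than about 15 weeks of cinacalcet can have in-gap or post-gap values. Criterion 108 asks for the 20110100 week 26 visit and does not mention completed treatment, so a subject who stopped cinacalcet early there could be a further exception.

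The conclusion rests on two assumptions: that weeks 11 and 15 run from first cinacalcet dose here, as the combined-studies completer row states, and that the SAP 6.2 windows apply on that clock. The primary safety analysis is unaffected. The change is still worth making, because the table as planned would present a largely pre-gap outcome as evidence on interruption.

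**What to change.** In SAP 10.6.2, for the dose-interruption analysis only:

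- Replace or supplement the weeks 11 and 15 endpoint with one anchored to the extension, for example a reduction of at least 30% from day 1 of cinacalcet to mean iPTH at extension-study weeks 11 and 15. Subjects with no value at either visit can be counted as non-responders, as in SAP 10.6.1.
- Restrict the analysis to subjects who received cinacalcet in a parent study.
- Keep the percent-change-over-time summary.
- Combined weeks 23 and 28 may be added, with a note that week 23 is pre-gap for 20110100 completers and that week 28 captures post-gap values only for short gaps. When both weeks are missing, the SAP 10.6.1 substitution of the last two titration-phase values could also bring in pre-gap results.

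The cost is one or two SAP sentences and minor programming. iPTH is already scheduled at extension weeks 11 and 15, so no new data are needed. The restriction lowers the planned maximum from 78 to 78 − 24 = 54, with the loss expected mainly in the no-interruption group.

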**Sensitivity analyses to assess the effect of missing data or non-compliance**

**Secondary endpoints for Study 20140159 only**

Secondary endpoint	Sensitivity Analyses	Planned for Interim or Final analysis
Achievement of $\geq 30\%$ reduction from baseline to mean iPTH during weeks 11 and 15 (SOC arm of Study 20130356 only)	
Inverse Probability Weighting (IPW) The missingness model will include study baseline iPTH, cCa, phosphorus, age group, sex, race, and AEs of nausea, vomiting and symptomatic hypocalcemia. Dialysis vintage, AE or IPD related to ending IP may be also included in the model depending on the EOIP reason observed in the study.
 
The final weighted pooled logistic regression model will include study baseline iPTH, cCa, phosphorus and age group. This analysis will be performed using the Study 20130356 SOC set.
	Final analysis only
	
Completer analysis: Only subjects completing 15 weeks of study in the Study 20130356 SOC set will be included in the analysis.
 
Subjects with no iPTH values during weeks 11 and 15 will be considered as nonresponders.
	Final analysis only
	
Per protocol analysis: Subjects in per protocol set who did not receive cinacalcet in the parent study and have at least one iPTH value during weeks 11 and 15 will be used.
	Interim and Final analyses
	
Nearest 2 imputation If no values are observed during weeks 11 and 15, the nearest two values at or after week 7 will be used, including unscheduled visit values, values prior to or after weeks 11 and 15. Subjects with no observed values at or after week 7 will be considered nonresponders.
	Final analysis only

Page 1 of 3

Secondary endpoints for Study 20140159 only

Secondary endpoint	Sensitivity Analyses	Planned for Interim or Final analysis
Achievement of $\geq 30\%$ reduction from baseline to mean iPTH during weeks 23 and 28 (SOC arm of Study 20130356 only)	IPW:  The IPW method is same as specified for the sensitivity of binary endpoint "Achievement of $\geq 30\%$ reduction from study baseline to mean iPTH during weeks 11 and 15".	Final analysis only
Achievement of a mean iPTH value $\leq 300$ pg/mL during week 23 and 28 (efficacy analysis set)	Completer analysis:  Only subjects with at least one iPTH value during week 23-28 will be included in the analysis.	Final analysis only
	Per protocol analysis:  Subjects from in per protocol set for Study 20140159 only who did not receive cinacalcet in the parent study and have at least one iPTH value during weeks 23 and 28 will be used for the endpoint defined for SOC arm of Study 20130356 only.  Subjects from the per protocol set for Study 20140159 only and with at least one iPTH value during weeks 23 and 28 will be used for the other endpoint.	Interim and Final analyses

Page 2 of 3

Secondary endpoints for Study 20140159 only

Secondary endpoint	Sensitivity Analyses	Planned for Interim or Final analysis
Percent change from baseline to mean iPTH during weeks 23 and 28 (SOC arm of Study 20130356 only)	Repeated measures mixed effect model:  The repeated measures model will include treatment group, study baseline age group, scheduled visits, and interaction of treatment group and scheduled visits. An unstructured covariance will be used for the model.	Final analysis only
Change in corrected total serum calcium from baseline to mean value during week 23 and 28 (efficacy analysis set)	Completer analysis:  Only subjects with at least one required lab value for the endpoint during week 23-28 will be included in the analysis.	Final analysis only
Change in serum phosphorus from baseline to mean value during week 23 and 28 (efficacy analysis set)	Per protocol analysis:  Subjects in both the Study 20130356 SOC set and per protocol set for Study 20140159 only and with at least one iPTH value during weeks 23 and 28 will be used for the endpoint defined for SOC arm of Study 20130356 only.  Subjects from the per protocol set for Study 20140159 only and with at least one corresponding lab value during weeks 23 and 28 will be used for other endpoints.	Interim and Final analyses

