**7.4 Study 20130356 SOC Set**

The Study 20130356 SOC set will be used for secondary endpoints that analyze subjects from Study 20130356 SOC arm only. The Study 20130356 SOC set includes all Study 20140159 enrolled subjects from Study 20130356 who did not receive cinacalcet prior to Study Day 1 of 20140159 and received at least one dose of cinacalcet in Study 20140159 and have at least one assessment after Study Day 1 of 20140159.

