### 7.7 Subgroup Analyses

The following characteristics **may** be used in the subgroup analyses planned for the primary, secondary **and safety** endpoints:

baseline age group in parent studies (6 to < 12 years old and 12 to < 18 years old for Study 20130356; 28 days to < 2 years old and 2 to < 6 years for Study 20110100)

gender (male and female)

race (black, white and other). If any category has **≤ 4 subjects**, the category will be pooled together with other category for summary purposes.

Tanner stage (1 and >1)

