#### Study20140159only

Proportion of subjects achieving the secondary endpoints of  $\geq 30\%$  reduction in iPTH from study baseline to mean value during weeks 11 and 15 will be reported with 95% CI based on 20130356 SOC Set. Subjects who have no iPTH values during weeks 11 or 15 will be considered non-responders.

Proportion of subjects achieving the secondary endpoints of  $\geq 30\%$  reduction in iPTH from study baseline to mean value during weeks 23 and 28 will be reported with 95% CI based on 20130356 SOC Set. For subjects who do not have a iPTH value during weeks 23 and 28, the mean of the last two available post-baseline values in the dose-titration phase will be used. If only one post-baseline value is available, this single value will be used. If no post-baseline value is available, the subject is considered a non-responder.

Summary statistics will be provided for percent change from study baseline to mean iPTH during weeks 23 and 28 based on 20130356 SOC Set, and change in corrected total calcium and change in serum phosphorus from study baseline to mean value during weeks 23 and 28 based on efficacy analysis set by treatment group in the parent studies. For subjects who are missing the efficacy measurement during weeks 23 to 28, the mean of the last two available post-baseline values in the dose titration phase will be used. If only one post-baseline value is available, this single value will be used. If no post-baseline value is available, the subject will be excluded from the analysis.

Proportion of subjects who achieve a mean iPTH value  $\leq 300$  pg/mL during weeks 23 and 28 will be provided based on efficacy analysis set by the treatment group in parent study with 95% CI. For subjects who do not have an iPTH value during weeks 23 and 28, the mean of the last two available post-baseline values in the dose-titration phase will be used. If only one post-baseline value is available, this single value will be used. If no post-baseline value is available, the subject is considered a non-responder.

**Summary statistics will be provided for serum cCa and phosphorus values at study baseline, week 11, and week 28 for all efficacy analysis set subjects.**

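### The SOC-set inverse-probability-weighting check puts 10 or 11 parameters on at most about 24 subjects, often has no finite fit, and does not say how it returns the endpoint proportion

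*SAP*

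**What the plan says.** SAP Section 10.6.1 defines the week 11/15 responder result as a proportion: "mean value during weeks 11 and 15 will be reported with 95% CI based on 20130356 SOC Set". Its missing-data rule is "Subjects who have no iPTH values during weeks 11 or 15 will be considered non-responders". The population is the Study 20130356 SOC set (SAP Section 7.4), meaning enrolled subjects from that study "who did not receive cinacalcet prior to Study Day 1 of 20140159" who were then dosed and had an assessment after Study Day 1.

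Section 10.6.2 adds four sensitivity analyses for this endpoint: IPW, completer, per-protocol and nearest-2 imputation. For IPW, "The missingness model will include study baseline iPTH, cCa, phosphorus, age group, sex, race, and AEs of nausea, vomiting and symptomatic hypocalcemia". In addition, "Dialysis vintage, AE or IPD related to ending IP may be also included in the model", depending on the reasons seen for ending investigational product. The outcome step reads: "The final weighted pooled logistic regression model will include study baseline iPTH, cCa, phosphorus and age group". For weeks 23 and 28, "The IPW method is same as specified for the sensitivity of binary endpoint" at weeks 11 and 15. The combined-studies table lists a similar missingness model and gives no outcome step.

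Section 7.7 has three race categories and says that if one is small, "the category will be pooled together with other category for summary purposes". It does not say whether this carries over to the weighting model.

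For the continuous endpoints, Section 10.6.2 plans a repeated-measures mixed model with treatment group, age group, visit and treatment-by-visit terms. It has no baseline laboratory value.

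**The concern.** IPW is the only planned check on the week 11/15 endpoint that models why values are missing. The completer analysis still counts a subject without a value as a non-responder, per-protocol keeps only subjects with a value, and nearest-2 substitutes values from other visits.

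A logistic model with nearly half as many parameters as subjects is likely to be separated: some combination of covariates perfectly sorts the missing from the observed, and maximum likelihood has no finite solution. The SAP states no penalty, reduced model, weight truncation or non-convergence rule. The analyst would then have to choose a remedy after seeing the data, or report weights that mean little.

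Even with a successful fit, a regression adjusted for four baseline covariates yields conditional log-odds, not the proportion in Section 10.6.1. The SAP does not define the word pooled, name a variance method, or describe a standardisation step.

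**Working it through.** **Subjects.** SAP Section 3.2 gives 48 + 30 = 78, which reproduces. Protocol Section 2.5.1 plans about 48 randomised 1:1, so the SOC arm is about 48 / 2 = 24. Protocol Section 4.1.1 (iPTH and corrected calcium thresholds) and SAP Section 7.4 can only lower this.

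**Parameters.** Intercept 1 + three laboratory values 3 + age group 1 (two bands in Study 20130356) + sex 1 + race 2 + three adverse events 3 = 11, or 10 if race is pooled to two levels. That is 24/11 = 2.2 to 24/10 = 2.4 subjects per parameter. With 3 to 8 missing there are 3/11 = 0.27 to 8/10 = 0.8 missing subjects per parameter.

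**Does a finite fit exist?** Let s = +1 for a missing subject and −1 for an observed one, with covariate vector x. Maximise Σ s·xᵀb subject to s·xᵀb ≥ 0 for every subject and −1 ≤ b ≤ 1. A positive optimum means separation, so no finite maximum-likelihood fit. Assumed, because the documents do not say: values missing at random with respect to the covariates; adverse-event rates 20/20/10% or 40/40/30%; race 60/20/20 or 80/10/10; 1500 data sets per cell. Subject level, n = 24:

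| Missing | No finite fit, 11 parameters | No finite fit, 10 parameters | Complete separation, 11 parameters | Complete separation, 10 parameters |
|---|---|---|---|---|
| 3 | 99.9-100% | 96-100% | 81-96% | 74-92% |
| 5 | 91-99% | 74-95% | 46-69% | 40-60% |
| 8 | 64-91% | 34-79% | 22-38% | 17-28% |

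A separate run (adverse events 25/25/15%, race 60/20/20, 1000 data sets) gave 100%, 96%, 85% and 65% for 11 parameters with 2, 5, 7 and 10 missing. At n = 20 the 11-parameter range was 83-100%, and at n = 16 it was 97-100%.

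**If pooled means one row per subject and visit.** With four visits and 2 to 10 dropouts among 24 subjects, the 11-parameter model still had no finite fit in 45-100% of data sets.

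**What the failed fit produces.** Under complete separation every observed subject's fitted probability of being observed tends to 1. Each weight, 1/probability, therefore also tends to 1 and nothing is reweighted. Under quasi-complete separation some weights stay finite. With 11 parameters the result then differed from the observed-case proportion by 2.5, 3.7 and 5.7 points on average with 3, 5 and 8 missing.

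**Final step.** The outcome model is logit P(response) = b0 + b1·iPTH + b2·cCa + b3·phosphorus + b4·age group. No coefficient is the marginal proportion. Recovering it needs averaging of fitted probabilities over a stated population, or direct use of Σwy / Σw. The SAP specifies neither.

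**Does a penalty help?** With the SAP's own list and three assumed missingness mechanisms, one of them driven by cCa, phosphorus and age group, penalisation lowered both bias and RMSE against the unpenalised fit every time. RMSE was 4.3-4.7, 6.4-7.1 and 9.2-11.0 points against 4.5-5.2, 6.8-7.7 and 10.6-12.2, with 3, 5 and 8 missing.

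**Best-case bound at weeks 11/15.** Counting the missing as responders lifts the main result by 3/24 = 12.5, 5/24 = 20.8 or 8/24 = 33.3 points.

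**Mixed model.** SAP Section 6.3 already defines baseline iPTH, corrected calcium and phosphorus. Assuming 25% dropout after week 7 that depends on baseline, and a correlation of 0.4-0.8, omitting baseline biases the week 23/28 mean change by 0.02-0.05 SD. For the SOC-only iPTH endpoint the treatment term has a single level.

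**The case against.** The strongest reply is that little depends on this check. The main week 11/15 rule is the worst case, and a check that collapses to the observed-case proportion is still informative. In one simulated setting the non-responder estimate was off by −3.9, −6.6 and −11.6 points and the observed-case estimate by +2.0, +3.4 and +5.1, so the two bracketed the truth. That stands. It limits the severity, but it does not make a model that often cannot be fitted a working sensitivity analysis.

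The missing rate is assumed, and a subject counts as missing only without iPTH anywhere in days 65-120 (the week 11 and 15 windows in SAP Section 6.2). That also stands, but fewer missing values make the fit less likely to exist.

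A reader might count only 8 parameters, by merging the adverse events into one term and pooling race. Failure would then drop to 12-30% with 8 missing. The SAP does not merge the events, and it gives race pooling only as a summary device.

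A reader might also infer that the cure is a short model, such as baseline iPTH and one any-event term. The documents do not support a particular short list, and its performance depends on the assumed mechanism. When missingness depended on cCa, phosphorus and age group, that model left 3.5, 5.4 and 9.3 points of bias against 3.5, 5.6 and 9.3 unweighted. It would also give up the SAP's clause on reasons for ending treatment, although transplant and parathyroidectomy are protocol-specified stops (Protocol Sections 3.1 and 8.2.1).

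SAP Section 9.3.1 requires a review of the pattern and impact of missing iPTH. That is a partial safeguard, not a rule for a failed fit.

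**Conclusion.** The point holds as a minor one. As listed, the SOC-set missingness model is too large for its data under every missing count tried, although with 10 parameters and 8 missing the failure rate can be as low as about a third. The rates rest on assumed missing counts, adverse-event rates and race mix. The missing step from regression to proportion rests on no simulation.

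The scope is narrow. A reader might infer that the responder results themselves are unreliable, but the documents do not support that. Section 10.1 makes all analyses descriptive, and IPW is planned for the final analysis only. The primary safety endpoint, the main secondary estimates and the interim analysis do not use it. The iPTH ≤ 300 pg/mL endpoint and the combined-studies IPW draw on up to 78 subjects, so size is less of a problem there; the unstated final step remains. The mixed-model gap is small and secondary.

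**What to change.** For the SOC-set IPW in SAP Section 10.6.2:

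- Keep the listed covariates and the clause on observed reasons for ending treatment, but fit the missingness model with a prespecified penalty (Firth or ridge).
- Replace the final pooled model by the weighted proportion Σwy / Σw. Give it a stated 95% CI: either Wilson with the Kish effective sample size (Σw)² / Σw², or a bootstrap that refits the weights in each resample. State the same final step for the combined-studies IPW.
- At weeks 11/15, report the best-case bound (missing counted as responders) beside the non-responder result.
- In the mixed model, add the baseline laboratory value for each endpoint and omit the treatment terms for the SOC-only iPTH endpoint.

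The cost is SAP wording and minor programming, with no new data. Penalisation removes only part of the bias, about a fifth to two fifths in simulation. The RMSE gain is small beside a 95% CI half-width of about 1.96 × √(0.25/24) = 0.20, or 20 points. The best-case bound is wide, which is an honest reflection of the sample size.
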